6.0 Number of Subjects

We will enroll approximately 110 patients in this study to include 55 patients for each randomized ‘treatment’ group. Please refer to section 12.0 for the justification behind this enrollment number.

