12.0 Data Management

Descriptive statistics by treatment group will be evaluated for all demographic and procedural characteristics. The goal of the study is to determine if there is a significant difference in the change in respiratory response immediately following administration of saline or povidone-iodine solution in patients undergoing strabismus surgery. The primary outcome is the difference between the peak to peak interval time from the capnograph measured before saline or povidone-iodine administration versus after administration. Pre-exposure peak to peak interval will be measured as the average time between peaks for five breaths prior to administration. Post-exposure peak to peak interval will only be evaluated as the time between the two peaks at saline or povidone-iodine administration. Differences in the change in peak to peak interval time between the saline and povidone-iodine exposure groups will be evaluated using a linear regression approach. The model will include a treatment effect and will additionally control for patient age, history of prematurity, and use of any pre-medication to account for other factors thought to be associated with respiratory rate. We anticipate no change in peak to peak interval time in the saline group with variability of ± 4 seconds. A sample size of 50 patients per treatment group (100 patients total) provides $>80\%$ power to detect an increase in change in peak to peak interval of 2.5 seconds in the povidone-iodine group compared to the saline group assuming equal variance between the two groups using a 2-sided test with significance level set at alpha = 0.05. If the variability of the povidone-iodine group is larger, for example a variability of 8 seconds, compared to 4 seconds in the saline groups we still have 80% power to detect an increase in the povidone-iodine group of approximately 4 seconds.

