Title: *The Effect of Povidone-iodine Ophthalmic Surgical Prep Solution on Respiration in Children Undergoing Strabismus Surgery with General Anesthesia*

NCT03349515

2018 August 15

Statistical Analysis: An *a priori* size calculation was conducted prior to the study. Assuming no change in the peak to peak end-tidal CO₂ interval time after drop instillation in the saline group, and a peak to peak interval time variability of ± 4 seconds, a sample size of 50 patients per group (100 patients total) provided $> 80\%$ power to detect an increase in change in peak to peak interval of 2.5 seconds in the povidone-iodine group compared to the saline group assuming equal variance between the two groups using a 2-sided test with significance level at $\alpha=0.05$.

Descriptive statistics by treatment group were estimated for patient and procedural characteristics. Differences in peak to peak interval time between the saline and povidone-iodine exposure groups were examined using a linear mixed model approach. Based on the *a priori* analysis plan, the model included fixed effects for treatment, breath number, a treatment by breath number interaction and a random subject effect to account for correlation between measures collected on the same subject. The model also controlled for factors thought to be associated with respiratory rate including age, pre-term birth, history of apnea, and breath duration prior to drop installation. Comparisons in breath duration between treatment groups at each of 15 breaths post-drop instillation were estimated from the model using Bonferroni corrected significance.

A secondary outcome of interest was occurrence of a significant change in respiration. Although apnea has been defined in the literature as a breath duration of 10 to 20 seconds, this definition is arbitrary and fails to account for within and between subject variability of breath duration. To account for within and between subject variability, we defined changes in respiration as having a breath duration greater than twice the inner-quartile range above the

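### Single-step Bonferroni over the 15 breath contrasts is valid but less powerful than Holm at the same family-wise error; the gain from Holm is small unless the response is sustained

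*SAP*

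**What the plan says.** The SAP's statistical analysis text fits a linear mixed model to breath duration, with treatment, breath number and their interaction as fixed effects and "a random subject effect to account for correlation between measures collected on the same subject". The arms are then compared; the comparisons "at each of 15 breaths post-drop instillation were estimated from the model using Bonferroni corrected significance". No step-down or other sequential procedure is named, and the family-wise level is not stated. The only alpha in the documents belongs to the sample-size calculation; Protocol section 12.0 gives it as "using a 2-sided test with significance level set at alpha = 0.05".

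The planning figures in the SAP are: "a sample size of 50 patients per group (100 patients total) provided" more than 80% power "to detect an increase in change in peak to peak interval of 2.5 seconds in the povidone-iodine group", with "a peak to peak interval time variability of ± 4 seconds" and "assuming equal variance between the two groups". They describe a single comparison.

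Protocol section 12.0 contains no family of breath tests. Its primary outcome sets one post-exposure interval against the mean of five baseline breaths, analysed by linear regression.

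**The concern.** With 15 comparisons and an assumed family level of 5%, single-step Bonferroni holds every p-value to 0.05/15, however many of the other contrasts have already been rejected. Holm's procedure relaxes the threshold after each rejection and needs no assumption about dependence. That suits contrasts estimated on the same children, which are correlated. If family-wise error is the criterion, Bonferroni therefore gives up some power that could be kept at little cost.

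What is at stake is which breaths are declared different between arms. If povidone-iodine lengthens several consecutive breaths, Bonferroni will on average declare fewer of them than Holm would from the same data.

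**Working it through.** **Inputs.** From the SAP: 15 contrasts; 50 per arm; difference 2.5 s; variability 4 s, read as the SD; equal variances. From the sample-size statements: two-sided alpha 0.05. Assumptions: the Bonferroni family also uses 0.05; the 2.5 s and 4 s figures apply at every affected breath; the contrasts have an exchangeable correlation of 0, 0.3 or 0.6.

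**Step 1: the plan's own figure.** The standard error of the difference is 4 × √(2/50) = 0.8 s, so the standardised effect is 2.5/0.8 = 3.125. At two-sided 0.05, power is Φ(3.125 − 1.960) = Φ(1.165) = 87.8% (87.2% with the noncentral t). The number needed for 80% is 2 × (1.960 + 0.842)² × 4²/2.5² = 40.2, so 41 per arm. The stated power of more than 80% is reproduced for a single comparison.

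**Step 2: one breath under Bonferroni.** The threshold is 0.05/15 = 0.00333, critical value 2.935. Power is Φ(3.125 − 2.935) = Φ(0.190) = 57.5%. With 55 per arm, the enrolment target in Protocol section 6.0, it is 63.4%.

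**Step 3: Holm's thresholds.** The ordered p-values are compared with 0.05/15, 0.05/14, 0.05/13 and so on up to 0.05, stopping at the first failure. Power for one breath is 57.5% at 0.05/15, 58.4% at 0.05/14, 59.3% at 0.05/13, 61.3% at 0.05/11 and 87.8% at 0.05. The thresholds relax slowly, so Holm gains much only after many rejections.

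**Step 4: why the error rate is kept.** Suppose m of the 15 null hypotheses are true. When Holm first rejects one of them, at most 15 − m hypotheses have already been rejected, so the threshold is at most 0.05/m. The chance that any of the m true nulls has a p-value that small is at most m × 0.05/m = 0.05, whatever the correlation. Every Holm threshold is at least 0.05/15, so nothing Bonferroni rejects is lost. The first threshold is 0.05/15 under both methods, so the chance of at least one rejection is identical.

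**Step 5: size of the gain.** Simulation, 100,000 runs per setting, 2.5 s at each affected breath, correlation 0.3:

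| Affected breaths | Bonferroni, power per affected breath | Holm | Extra affected breaths declared, on average |
|---|---|---|---|
| 1 | 57.5% | 57.5% | 0 |
| 2 | 57.6% | 58.2% | 0.01 |
| 3 | 57.5% | 58.4% | 0.03 |
| 5 | 57.5% | 59.6% | 0.10 |
| 10 | 57.4% | 63.1% | 0.57 |
| 15 | 57.5% | 70.3% | 1.9 |

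The last column is the gain in power times the number of affected breaths, for example 0.128 × 15 = 1.9. Across correlations 0 to 0.6, Holm gives 59-60% for five affected breaths, 63-64% for ten and 69-71% for 15. With a first-breath effect of 5 s and later effects of 2.5 s (correlation 0.3), power at the later breaths rises from 57.7% to 58.5% with two breaths affected, 57.4% to 59.9% with five and 57.5% to 63.7% with ten.

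**Step 6: error rates.** Holm rejected everything Bonferroni rejected in every run. With 15 independent true nulls, family-wise error is 1 − (1 − 0.05/15)^15 = 0.0489 by formula and 0.0487 in simulation for both methods. With no affected breaths and correlation 0.6, the expected number of false rejections was 0.0491 under Bonferroni and 0.0539 under Holm.

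**The case against.** The strongest reply is that nothing here is wrong. Bonferroni is valid under any correlation, and preferring Holm is a matter of efficiency. That stands.

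The size of the gain also favours the reply. The documents point towards a short response: Protocol section 12.0 looks at the interval at the moment of administration, and section 2.0 refers to apnea of short duration. For one to five affected breaths Holm adds 0 to about 2 percentage points. Most of the drop from 87.8% to 57.5% comes from dividing alpha by 15, and Holm recovers little of that for a short response. This stands too. The larger gains need an effect over ten or more breaths, which nothing in the documents suggests.

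Bonferroni also gives something in return. It bounds the expected number of false rejections at 15 × 0.05/15 = 0.05, which Holm does not, and it has simple simultaneous intervals that agree with its tests. Holm therefore dominates on family-wise error only.

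Three stronger readings are tempting, and the documents support none of them.
- A reader might infer that Bonferroni misses affected breaths after the first. On the planning figures it still finds a 2.5 s effect at a later breath about 57% of the time.
- A reader might infer that the duration of the response is understated. Neither document defines duration as an outcome or reads it from a count of significant breaths, and the 15 estimates are the same under either procedure.
- A reader might infer that the planned primary test is affected. The primary outcome in Protocol section 12.0 is one interval with no multiplicity family. That the SAP describes a different model is a separate matter.

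**Conclusion.** The point holds as a minor efficiency improvement. For the same family-wise error, Holm declares every breath that Bonferroni declares and sometimes more, whatever the correlation; this does not depend on the planning figures. The size of the gain does. It rests on a 5% family level, 50 per arm, SD 4 s and 2.5 s at every affected breath, figures planned for a single comparison, and on a correlation that the documents do not give. Under those assumptions the gain is nil for one affected breath, about 2 points for five, about 6 for ten and 12 to 14 if all 15 are affected. The calculation uses z-tests. Adjustment for the SAP's covariates would shift the absolute power but not the ordering of the two methods. The conclusion on whether any breath differs between arms is the same under both.

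**What to change.** Report Holm step-down adjusted p-values, family-wise 5%, for the 15 breath contrasts, state that family level explicitly, and keep the Bonferroni simultaneous confidence intervals for the estimates.

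Timing decides how to present this. The SAP is written in the past tense and already says that no child given saline had a change in respiration, so a switch now would be a choice made after data were seen. The Holm results should therefore stand beside the Bonferroni results, labelled as added after the data were seen, and should not replace them. In a future protocol Holm could simply be named in advance.

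The cost is one line of text and a re-adjustment of p-values already in hand. There are two downsides. A Bonferroni interval may include zero for a breath that Holm declares, which needs a sentence of explanation. The bound of 0.05 on the expected number of false rejections no longer applies to the Holm results.
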